gMG treatments at or following enrollment (excluding efgartigimod)	
 Drug name, dose, start and stop dates 
 Acetylcholinesterase inhibitors Corticosteroids Other Immunosuppressants (specify) Monoclonal antibodies (specify) Plasmapheresis/plasma exchange acute Plasmapheresis/plasma exchange chronic IVIg therapy acute IVIg therapy chronic Other 	✓	✓

Category	Variables	Baseline	Follow up
Efgartigimod treatment	
 • Date of administration • Reason for interruption during cycle of treatment • Reason for permanent discontinuation whilst on study 	✓	✓
Other comedications at or following enrollment for conditions other than gMG	
 • Drug name, start and stop dates • Indication 	✓	✓
Live/attenuated vaccinations 2 months prior to enrollment to 2 months after last Vyvgart dose	
 • Live/attenuated vaccine 
 ○ Vaccine ○ Date 	✓	✓
Adverse Events (AEs)/Serious Adverse Events (SAEs)	
 • AEs, SAEs 		✓
Events of interest	See Table 2		✓

*All variables will be collected ONLY if available as part of routine clinical practice

A patient will be considered to be an efgartigimod exposed patient if he/she has received at least one dose of efgartigimod.

Additionally, taking into account the variable follow up time and time interval between cycles, the following will be measured for efgartigimod:

- Number of administrations per year
- Total duration of the exposure
- Total number of administrations

The exposure time window of efgartigimod is 56 days +/-3 days after the last dose.

Events of interest in this study will be pre-specified as per [Table 2](#) below.

Table 2: Pre-specified events of interest

Event of interest	Definition	Measurement
Serious infection	Any serious adverse event coded to the Medical Dictionary for Regulatory Activities (MedDRA) System Organ Class (SOC) of Infection and Infestation. See Section 11 for definition of Serious.	Proportion of patients who report serious infections during the course of the study in the efgartigimod treated cohort compared to the non-efgartigimod cohort. Incidence rate of serious infections per patient-years exposed in the efgartigimod treated cohort compared to the non-efgartigimod cohort.

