
AEs (serious and non-serious) in patients treated with monoclonal antibodies
	
Patients receiving monoclonal antibodies other than FcRn (e.g., adalimumab, tocilizumab, ixekizumab, rituximab) within 6 months prior to efgartigimod administration.
	
Proportion of AEs/SAEs reported in patients treated with monoclonal antibodies vs patients not treated with monoclonal antibodies in the efgartigimod cohort.
 
Incidence rate of AEs/SAEs per patient-years exposed in patients treated with monoclonal antibodies vs patients not treated with monoclonal antibodies in the efgartigimod cohort.

AEs (serious and non-serious) in patients treated with live attenuated vaccine
	
Patients receiving live/attenuated vaccine (e.g., live-attenuated flu vaccine, measles, mumps and rubella, polio, smallpox, chickenpox, yellow fever, Japanese encephalitis, shingles, rotavirus) in the period of 4 weeks prior to or 2 weeks after efgartigimod administration.
	
Proportion of AEs/SAEs reported in patients who have received live/attenuated vaccine vs patients who have not received live/attenuated vaccine in the efgartigimod cohort.
 
Incidence rate of AEs/SAEs per patient-years exposed in patients who have received live/attenuated vaccine vs patients who have not received live/attenuated vaccine in the efgartigimod cohort.

AEs (serious and non-serious) in patients with moderate to severe renal impairment
	
Moderate renal impairment: eGFR 30-59 mL/min/1.73 m² Severe renal impairment: eGFR < 30 mL/min/1.73 m²
	
Proportion of AEs/SAEs reported in patients with moderate renal impairment vs patients who have normal renal function in the efgartigimod cohort.
 
Incidence rate of AEs/SAEs per patient-years exposed in patients with moderate renal impairment vs patients who have normal renal function in the efgartigimod cohort.
 
Proportion of AEs/SAEs reported in patients with severe renal impairment vs patients who have normal renal function in the efgartigimod cohort.

		Incidence rate of AEs/SAEs per patient-years exposed in patients with severe renal impairment vs patients who have normal renal function in the efgartigimod cohort.
--	--	--

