Balance of the baseline measures, including age, MG-ADL score and region matched at enrollment and other demographic and disease characteristics, will be assessed. The imbalanced measures which are considered to be potential confounders based on clinical judgement will be added to the above base models as covariates. If a large number of imbalanced potential confounders are identified after the enrollment is complete, a propensity score method will be applied instead. More details will be given in the SAP.

Subgroup analyses will be performed using descriptive statistics on the subset of patients who remained on efgartigimod throughout the duration of the PASS. In addition, subgroup analyses of treatment cycle per year or administration per year (four administrations in one cycle if not interrupted), subgroup analyses of time since the last administration of efgartigimod prior to the event occurrence in intervals of every 4 weeks will be performed, and subgroup analysis of patients using efgartigimod as add-on or single treatment will be performed if sample size allows. Since one patient may have multiple same events with different time to the last administration, one patient may be assigned to multiple time intervals.

Events of Interest

Statistical analysis of malignancy and other events of interest will follow the same method as those for serious infections

Exploratory objectives

Descriptive statistics will be used to summarise the long-term safety of efgartigimod for specific subgroups. The number and percentage of patients with AEs/SAEs will be presented. The rate per person-year exposure with a 95% CI will be constructed using asymptomatic normal approximation. This will be done for the following subgroups:

- immunocompromised patients and immunocompetent patients.
- patients treated with monoclonal antibodies and patients not treated with monoclonal antibodies.
- patients who have received live/attenuated vaccine and patients who have not received live/attenuated vaccine.
- patients with moderate to severe renal impairment and patients with normal renal function or mild renal impairment.

Missing values

No imputation will be applied to occurrence of serious infection, malignancy or other safety events.

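### The live-vaccine comparison (and, on some readings, the monoclonal-antibody one) sorts patients by an exposure that may fall at any time on treatment but sets no matching window for the events counted

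*Protocol*

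**What the plan says.** Protocol Table 2 (section 9.3) classes an efgartigimod-cohort patient as a live-vaccine patient if the vaccine was given "in the period of 4 weeks prior to or 2 weeks after efgartigimod administration". An antibody patient is one who received another monoclonal antibody "within 6 months prior to efgartigimod administration". Neither row says whether the first, any or the last administration is meant.

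The vaccine measures are the "Proportion of AEs/SAEs reported in patients who have received live/attenuated vaccine vs patients who have not received live/attenuated vaccine in the efgartigimod cohort" and a rate, the "Incidence rate of AEs/SAEs per patient-years exposed in patients who have received live/attenuated vaccine", set against unvaccinated patients. The antibody row has the same form: "Proportion of AEs/SAEs reported in patients treated with monoclonal antibodies vs patients not treated with monoclonal antibodies in the efgartigimod cohort". Section 9.7 (exploratory objectives) repeats the split as "patients who have received live/attenuated vaccine and patients who have not received live/attenuated vaccine" and reports patients with AEs/SAEs and a rate per person-year.

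Three other statements bear on this:
- Table 1 collects "Live/attenuated vaccinations 2 months prior to enrollment to 2 months after last Vyvgart dose", so a qualifying vaccination can occur at any point on treatment.
- Section 11 collects AEs from consent to the end of participation. Section 9.1 gives 5 to 10 years of follow-up, whether or not efgartigimod continues.
- Section 9.3 adds that "The exposure time window of efgartigimod is 56 days +/-3 days after the last dose". It does not link this window to the vaccine or antibody rows.

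**The concern.** Classification has a time window but the outcome has none. A patient vaccinated in year 6 becomes a vaccinated patient, and nothing in Table 2 or section 9.7 keeps that patient's AEs and person-time from years 0 to 6 out of the vaccinated group.

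Membership also depends on opportunity. Vaccinations are captured only until 2 months after the last dose, so patients who stay on treatment longer, or have more cycles, are more likely to be classed as vaccinated. The groups then differ in treatment duration by construction.

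Section 7 lists these populations as missing information in the EU risk management plan. The practical danger is that a ratio close to 1, produced mainly by time unrelated to the vaccine, is read as evidence of safety.

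**Working it through.** **Plan's own figures.** The protocol gives no number for these subgroups. Its power figure concerns the cohort comparison: 84% for 20% versus 31% with 270 per arm, which recomputes to 83.7%. It does not bear on this point.

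**Opportunity to be classed as vaccinated.** Section 7 describes a cycle as weekly infusions for 4 weeks, so the first and last infusions are 3 weeks apart. If any administration counts, one full cycle opens 4 + 3 + 2 = 9 weeks in which a vaccination qualifies. Three well-separated cycles open 27 weeks. The chance of classification grows with treatment.

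**Dilution of the rate ratio.** Let w be the time at raised risk, T the time counted and RR the true ratio within w. With a constant background rate, the ratio seen over all time counted is 1 + (RR − 1) × w/T.

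Assumptions: one vaccination per patient; w = 42 days (the length of the classification window) or 56 days; T = 5, 7.5 or 10 years. The protocol gives 5 and 10; 7.5 is the midpoint, assuming uniform enrolment and no drop-out.

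| w | T (years) | w/T | RR 3 seen as | RR 5 seen as |
|---|---|---|---|---|
| 42 days | 5 | 2.3% | 1.05 | 1.09 |
| 42 days | 7.5 | 1.5% | 1.03 | 1.06 |
| 42 days | 10 | 1.2% | 1.02 | 1.05 |
| 56 days | 5 | 3.1% | 1.06 | 1.12 |
| 56 days | 7.5 | 2.0% | 1.04 | 1.08 |
| 56 days | 10 | 1.5% | 1.03 | 1.06 |

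**If only efgartigimod-exposed time counts.** Suppose half of 7.5 years is exposed (assumption), so T = 3.75 years, or 1,370 days. Then 42/1370 = 3.1% gives 1.06 (RR 3) and 1.12 (RR 5), and 56/1370 = 4.1% gives 1.08 and 1.16.

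**Share of events outside the window.** This is (T − w)/[(T − w) + RR × w]. With T = 7.5 and w = 0.115 years, it is 7.385/(7.385 + 0.345) = 96% for RR 3 and 7.385/(7.385 + 0.575) = 93% for RR 5.

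**Proportion of patients with an event.** Section 9.5 reports serious infection in 6.2% over a mean of 1.7 years in ADAPT+. At a constant rate this is −ln(0.938)/1.7 = 0.038 per year.
- By 7.5 years, 1 − exp(−rate × T) gives 24.6% of unvaccinated patients, against 25.3% (RR 3) or 25.9% (RR 5) of vaccinated patients with w = 42 days.
- Follow-up alone moves the same proportion from 17.2% at 5 years to 31.4% at 10 years.
- For any AE the proportion saturates. Section 7 gives infections in 46.4% on efgartigimod and 37.3% on placebo; taken as half-year figures at a constant rate, these exceed 99% by 5 years.

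**Monoclonal antibodies.** For illustration only, take one course with 6 months at raised risk. Over 5, 7.5 and 10 years, RR 3 shows as 1.20, 1.13 and 1.10, and RR 5 as 1.40, 1.27 and 1.20. Table 2's 6 months is a look-back for classification, not a stated risk period. With ongoing antibody treatment there is little or no dilution.

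**The case against.** **Whole-study counting is not stated.** A reader might infer that the plan says AEs are counted over the whole study in these rows. It does not. That wording appears in the serious-infection, malignancy, AE and SAE rows and is absent here, and the person-time wording may limit the rate to efgartigimod-exposed time. This stands as a limit on the claim. But efgartigimod-exposed time is still not vaccine-exposed time, the limit does not touch the proportion, and the half-exposed example remains heavily diluted.

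**Details are left to the SAP.** Section 9.7 and the ENCePP checklist (exposure section) both say so. An event window alone could be left there. The patient-level received/not-received measure, however, is already written in Table 2 and section 9.7, and an SAP that followed it would inherit the problem.

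**Antibody exposure need not be brief.** This stands. Table 1 records start and stop dates, which allows ongoing use. If the first administration is meant, status is fixed at baseline and no study event on efgartigimod precedes classification.

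**Case-level safeguards exist.** This also stands. Section 11.1 requires a causality assessment for every AE and makes suspected drug interactions and suspected transmission of an infectious agent reportable. Section 9.7 tabulates AEs by SOC and PT.

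**The objectives are exploratory and descriptive.** True, and this keeps the point below a critical one. A descriptive comparison still needs to describe the time that the question concerns.

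**Conclusion.** The point holds for the live-vaccine objective and, to a smaller and reading-dependent extent, for the antibody objective. With no matching event window, the plan as written credits pre-vaccination events and person-time to the vaccinated group and favours longer-treated patients for that group. A three- to five-fold short-term rise shrinks to about 1.02 to 1.09 (6 weeks at risk) or 1.03 to 1.12 (8 weeks) over 5 to 10 years. These figures rest on one vaccination per patient, a constant background rate, an assumed risk period and all follow-up being counted.

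Two stronger readings are not supported. A reader might conclude that no signal could be found; very large effects, or individual cases picked up through causality and special-situation reporting, could still be seen. A reader might also extend the criticism to immune status; no defect is shown there, and Table 1 already records it at baseline and follow-up.

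**What to change.** In Table 2 and section 9.7:
1. State which efgartigimod administration (first, any or last) defines vaccine and antibody status.
2. Make both statuses time-updated. Events and person-time count as co-exposed only from the date both exposures are present and within a pre-specified event window. The sponsor sets its length and adds a sensitivity window.
3. Assign all other efgartigimod-cohort time, including the same patient's earlier time, to the reference.
4. Define the denominator of the exposed patient-years.
5. List in-window AEs/SAEs per patient.

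Table 1 already collects vaccine dates, antibody start and stop dates and efgartigimod administration dates, so the cost is wording and programming. The downside is few in-window events and wide intervals, which the report should show plainly.

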9.4 Data Sources

Data will be extracted from the patient's medical records by site personnel. Once written informed consent has been obtained, study site personnel will complete the data collection for each patient. Follow-up data for patient visits will be recorded in the patient chart in accordance with the clinical site's standard of care or clinical judgment. All data will be extracted from medical records and entered into the EDC on an ongoing basis.

The technologies used for this study (e.g., EDC) will be compliant with Title 21 Code of Federal Regulations (CFR) Part 11, EudraLex Annex 11, the General Data Protection Regulation (GDPR), and local data privacy requirements, and will be evaluated on an ongoing basis throughout the duration of the study to ensure upgrades are made when necessary.

If feasible, data may also be collected from the MyaReg.

9.5 Study Size

A sample size of 340 patients in each of the two cohorts is proposed (680 patients in total). Recruitment will be over a 5 year period and patients will be followed for 5 years from the time the last patient is enrolled. Thus maximum follow up will be 10 years.

The estimated prevalence rate for MG is 77.7 per million persons (range 15-179) and the estimated incidence rate is 5.3 per million person-years (range 1.7–21.3).

Myasthenia gravis occurs in both genders, at all ages, and in all races. However, for sample size calculations it is proposed to use the reported serious infection prevalence in MG patients.

Statistical analysis in this study will be descriptive and exploratory, and not aimed to confirm or reject predefined hypotheses.

Sample size calculation is driven by the precision of the estimated incidence proportion of serious infection assuming similar incidence proportion to the background.

In a population-based cohort study of 3823 MG patients ([Kassardjian 2020](#)) followed for a mean of 5.4 (Standard Deviation [SD]=3.8) years, 33.4% of patients experienced a serious infection which included both emergency department visits and hospitalisation with primary diagnosis of infection. In a retrospective chart review of 358 MG patients ([Prior 2018](#)) over a 10-year period, 19% of patients experienced infection. In the argenx-sponsored ADAPT+ study final analysis with 145 efgartigimod patients followed for a mean of 1.7 years (SD=0.7), 6.2% of patients experienced at least one serious infection (serious adverse event with SOC term "Infections and Infestations").

For the current study, serious infection incidence proportion is assumed to be 20% considering varied follow-up time and definitions of serious infection in the literature and argenx-sponsored trial.

The sample size needed to achieve a 5% precision (half-width) is presented in Table 3 below with the following assumptions:

- An incidence proportion of 20% for serious infections among patients receiving efgartigimod.
- Two-sided 95% exact binomial confidence limits based on the Clopper-Pearson method.

Table 3: Precision calculations for different incidence proportions

Number of Patients	Expected Incidence Proportion	Expected Number of Patients with Event*	Lower Limit of 95% Confidence Interval (CI) of Observed Incidence Proportion	Upper Limit of 95% CI of Observed Incidence Proportion
215	15%	32	10.5%	20.5%
245	18%	44	13.4%	23.4%
264	20%	52	15.3%	25.3%
282	22%	62	17.3%	27.3%
306	25%	76	20.2%	30.2%

*Rounded down to the nearest whole number

A sample size of 270 is recommended to achieve 5% precision (half width). Considering a drop-out rate of 20%, 340 patients in each arm are needed.

To provide further justification about detecting potential increased risk given the calculated sample size above, the power calculation is presented in Table 4 below assuming 20% incidence proportion in the comparator arm and varied increased incidence proportions in the treatment arm with two-sided 0.05 alpha level using normal approximation. With 270 patients who complete the study in each arm, there is 84% power to detect an 11% risk increase.

Table 4: Power calculations to detect potential increased risk

Risk Increase	Expected Proportion for Comparator Arm	Expected Proportion for Treatment Arm	Completion Status	Sample Size in Each Arm	Power
9%	20%	29%	Completers Only	270	69%
10%	20%	30%	Completers Only	270	77%
11%	20%	31%	Completers Only	270	84%
12%	20%	32%	Completers Only	270	89%
9%	20%	29%	Completers + 30 Drop-outs	300	73%
10%	20%	30%	Completers + 30 Drop-outs	300	81%
11%	20%	31%	Completers + 30 Drop-outs	300	88%
12%	20%	32%	Completers + 30 Drop-outs	300	92%
9%	20%	29%	Completers + 60 Drop-outs	330	77%
10%	20%	30%	Completers + 60 Drop-outs	330	85%
11%	20%	31%	Completers + 60 Drop-outs	330	90%
12%	20%	32%	Completers + 60 Drop-outs	330	94%

Owing to the study design with 5-year enrollment and 5-year follow-up, patients will be followed between 5 to 10 years. A discontinued patient enrolled early and discontinued not soon after enrollment will be included in the analysis with possible long follow-up time. For example, the first enrolled patient discontinued at year 6 will have longer follow-up time than the last enrolled patient who has only 5-year

follow-up at maximum. Therefore, early discontinued patient may still contribute high-quality information with acceptable follow-up time to the analysis. Additional power analysis is provided in Table 4 assuming 270 completers +30 and +60 early discontinued patients being included in the analysis, and there is >80% power to detect a 10% risk increase.

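### Table 4 gives early drop-outs the incidence of patients followed 5 to 10 years, so the claim of more than 80% power for a 10-point increase is overstated by about 2 to 4 points

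*Protocol*

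**What the plan says.** Section 9.5 sizes the study on precision: "A sample size of 270 is recommended to achieve 5% precision (half width") at 20% incidence, raised to 340 per cohort for 20% drop-out. The 20% is presented as a judgement: "serious infection incidence proportion is assumed to be 20% considering varied follow-up time and definitions of serious infection in the literature". The sources are a population cohort (33.4% at a mean of 5.4 years), a chart review (19% over a 10-year period, for infection rather than serious infection) and the sponsor's extension study, in which "6.2% of patients experienced at least one serious infection" at a mean of 1.7 years.

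Table 4 is offered as further justification. It is computed "assuming 20% incidence proportion in the comparator arm", "with two-sided 0.05 alpha level using normal approximation". The text first reports completers: "With 270 patients who complete the study in each arm, there is 84% power to detect an 11% risk increase". It then adds rows "assuming 270 completers +30 and +60 early discontinued patients being included in the analysis" and concludes from them that "there is >80% power to detect a 10% risk increase". All twelve rows use 20% against 29–32%, whether or not drop-outs are included. The support for counting drop-outs in full is that some leave late; the example is the first enrolled patient leaving at year 6.

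**The concern.** Incidence proportion grows with time observed. A patient who leaves early has had less time to have a serious infection than one followed for 5 to 10 years, so drop-outs should carry a lower expected proportion and a smaller absolute difference between cohorts. Table 4 lets them raise the sample size without diluting the difference. For a 10-point increase, the rows with drop-outs are also the only ones above 80%.

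At stake is how a finding of no difference would be read. If readers are told that the study had more than 80% power for a 10-point excess, they may take that excess as better excluded than the design supports. The logistic model in section 9.7 has no follow-up term, so it works on the same scale as Table 4.

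**Working it through.** **Inputs from section 9.5:** 20% versus 30%; two-sided 0.05; 270 completers; 30 or 60 drop-outs; follow-up of 5 to 10 years.

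**Step 1. Reproduce Table 4.** Unpooled normal approximation: power = Φ(Δ/SE − 1.96), with SE = √[(p₁(1−p₁) + p₂(1−p₂))/n].
- n = 270: SE = √(0.37/270) = 0.0370; 0.10/0.0370 − 1.96 = 0.741; power 77.1% (stated 77%).
- n = 300: 81.3% (stated 81%).
- n = 330: 84.8% (stated 85%).

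With pooled null variance the figures are 76.7%, 80.9% and 84.5%. All twelve rows reproduce within one point.

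**Step 2. Incidence in drop-outs.** Assumptions: constant hazard λ, and leaving time uniform over planned follow-up T. Expected incidence is 1 − (1 − e^(−λT))/(λT). Where completer incidence is 20%, λT = −ln 0.8 = 0.2231, giving 1 − 0.20/0.2231 = 10.4%. Where it is 30%, λT = −ln 0.7 = 0.3567, giving 1 − 0.30/0.3567 = 15.9%. Averaging over T uniform on 5 to 10 years gives the same two figures.

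**Step 3. Power with those incidences.**
- 270 + 30: (54 + 30 × 0.104)/300 = 19.0% versus (81 + 30 × 0.159)/300 = 28.6%. Difference 9.55 points, SE 0.0346, power 78.9% (stated 81%).
- 270 + 60: 18.3% versus 27.4%. Difference 9.19 points, SE 0.0325, power 80.7% (stated 85%).

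**Step 4. Sensitivity to timing.** Let drop-outs have a fraction f of completer follow-up, with incidence 1 − (1−P)^f. Power with pooled variance:

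| f | +30 | +60 |
|---|---|---|
| 0 | 75.3% | 74.2% |
| 0.25 | 77.2% | 77.9% |
| 0.5 | 78.8% | 80.7% |
| 0.75 | 80.0% | 82.9% |
| 1 (as in Table 4) | 80.9% | 84.5% |

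The +30 row reaches 80% at f ≈ 0.76 (pooled). With unpooled variance it does so at f ≈ 0.68: 19.4% versus 29.1%, difference 9.74 points, SE 0.0348. The threshold is therefore roughly 70–76%. The +60 row reaches 80% at f ≈ 0.43 (pooled).

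**Step 5. The 20% on the study's time scale.** At constant hazard, rate = −ln(1−p)/t, averaged over T uniform on 5 to 10 years:
- Chart review: −ln(0.81)/10 = 0.0211 per year, about 15% (if every patient was followed for 10 years).
- Extension study: −ln(0.938)/1.7 = 0.0377 per year, 24.5% on average (17.2% at 5 years, 31.4% at 10).
- Population cohort: −ln(0.666)/5.4 = 0.0753 per year, about 43%.

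The hazard ratio implied by 20% versus 30% is ln 0.7/ln 0.8 = 1.60. For 270 completers (unpooled):

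| Base incidence | Power, +10 points | Power, hazard ratio 1.60 |
|---|---|---|
| 20% | 77% | 77% (versus 30%) |
| 24.5% | 73% | 85% (versus 36.2%) |
| 43% | 65% | 97% (versus 59.3%) |

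**Step 6. Exact 95% half-width (Clopper-Pearson).** With 270: 4.9 points at 20%, 5.3 at 24.5%. With 340: 4.4 and 4.7.

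**The case against.** The best defence is that the power figures are secondary. The protocol calls its analysis descriptive and sizes the study on precision. It prints the completers-only rows, counts at most 60 of about 70 expected drop-outs, and argues that some drop-outs leave late. If they average three quarters of completer follow-up, both rows are at about 80% or above. The uniform timing used here is an assumption, and under it the 60-drop-out row still just passes 80%.

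Most of this stands, and it keeps the point small. It does not rescue the sentence, which is unconditional and gives no drop-out timing. Section 9.7 also plans models to test the difference between cohorts. The Cox model handles unequal follow-up in the analysis but does not correct a power figure computed from proportions.

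A reader might go further in four ways that the documents do not support:
- **That 20% is too low throughout.** It lies inside the roughly 15–43% implied by the three sources. The extension study gives 17.2% at 5 years and passes 20% only at about 5.9 years. It is also small: assuming 9 events in 145, its 95% interval projects to about 12–42% at 7.5 years.
- **That a higher base incidence means less power.** This holds only for a fixed absolute difference. At a fixed hazard ratio, power rises.
- **That 5-point precision is overstated in general.** The Safety Population is not limited to completers. With about 340 analysed, the target is met at 20% and at 24.5%. Lower incidence in drop-outs would narrow the interval.
- **That the scale of the risk increase is hidden.** Table 4 prints both proportions on every row, so percentage points are plain.

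**Conclusion.** The point holds in a limited form. The drop-out rows of Table 4 use an incidence that suits only patients with full follow-up, and the claim of more than 80% power for a 10-point increase depends on those rows. At the protocol's own 20%, under constant hazard and uniform drop-out, power is about 79% with 30 drop-outs and 81% with 60, which is about 2 and 4 points below the stated figures. A fair summary is about 77–81%. Much earlier drop-out would bring power below the completers-only figure; late drop-out would bring it close to what is stated.

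The choice of 20% is a declared judgement and is not shown to be wrong. The 5-point half-width with 270 patients is specific to incidence near 20%, as Table 3 itself shows by requiring 306 at 25%. Nothing here calls for a larger study.

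**What to change.** In section 9.5, keep 340 per cohort and:

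1. Recompute the drop-out rows of Table 4 with partial-follow-up incidence, and state the drop-out timing assumed.
2. Restate the power sentence as about 77–81% power for a 10-percentage-point increase (20% versus 30%).
3. Add a sensitivity display that converts the three sources to the 5-to-10-year scale (about 15%, 24.5% and 43% at constant hazard). Show power both for a fixed 10-point difference and for a fixed hazard ratio of about 1.6. Note that the chart review reports infection and gives no follow-up per patient.
4. State that the half-width with 270 patients is 4.9 points at 20% and 5.3 at 24.5%, and with about 340 analysed 4.4 and 4.7.

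The cost is some text, a revised Table 4 and one small added table. No extra patients or data are needed, and the stated power becomes slightly less favourable.
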